12.2.1. Hematology

In order to investigate the maximal degree of myelosuppression, absolute neutrophil counts (ANC), white blood cell counts (WBC), platelet counts, and hemoglobin will be summarized by worst grade overall for each subject. Frequencies and percentages of Grade 1, 2, 3, 4 in each category will be tabulated. A column with pooled Grade 3/4 frequencies and percentages will also be displayed. In a separate table, the frequencies and percentages of subjects with at least one Grade ≥ 1 or one Grade 3 or 4 hematological toxicity will be presented.

For erythrocytes and hematocrit normal ranges will be used to determine the categories of below and above normal ranges.

12.2.2. Biochemistry

Creatinine, creatinine clearance, protein, albumin, total bilirubin, alkaline phosphatase, alanine aminotransferase (SGPT), aspartate aminotransferase (SGOT), glucose, sodium, potassium, chloride, total calcium, calcium, ionized, total magnesium, magnesium, ionized will be

summarized by the worst grade in each treatment cycle and by the worst grade overall. The worst grade of each biochemistry parameter will be calculated for each subject. Frequencies and percentages of Grade 1, 2, 3, 4 in each category will be tabulated. A column with pooled Grade 3 or 4 frequencies and percentages will also be displayed. In a separate table, the frequencies and percentages of subjects with at least one Grade ≥ 1 or one Grade 3 or 4 hematological or biochemistry toxicity will be presented.

For urea, urea nitrogen, uric acid, bicarbonate normal ranges will be used to determine the categories of below and above normal ranges.

12.3. Vital Sign/Physical Examination Measurements

For vital signs, the shift from baseline to worst during the treatment in below, within, and above the normal ranges will be displayed in cross-tabulations for each treatment. Summary statistics (N, Mean, Standard Deviation, Median, Minimum, and Maximum) of observed values and change from baseline values will be presented.

12.4. Electrocardiograms

The overall ECG interpretation will be summarized by presenting the number and percentage of subjects with ‘Normal’, ‘Abnormal, not clinically significant’, and ‘Abnormal, clinically significant’ by treatment. The shift from baseline to worst during the treatment in the overall ECG interpretation will be displayed in cross-tabulations for each treatment.

QT analysis

Descriptive analysis by sex of the length of the QT intervals among the subjects will be provided. The QTc-interval at baseline, Day 1 of concomitant treatment, Cycle 2 Day 1 of adjuvant treatment will be summarized, including change from baseline. The average of the readings at each visit will be used for the summary.

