### 5.6.4 ECG with use of Marizomib

To date, there has been no signal of a safety issue with ECG abnormalities including prolonged QTc with marizomib. There has been no signal of ECG abnormalities in patient treated with marizomib. However, a thorough

analysis of the QT/QTc data has not yet been submitted to the US FDA. Thus additional ECGs will be collected in the marizomib arm of the study.

12-lead ECGs will be collected for all subjects on marizomib at specified timepoints: baseline, Day 1 of concomitant treatment, Cycle 2 Day 1 of adjuvant treatment, and as clinically indicated and will be assessed locally.

ECGs on Day 1 of concomitant treatment and Cycle 2 Day 1 of adjuvant treatment will be collected within 15 minutes after end of MRZ infusion. The standard 12-lead ECGs (including heart rate, PR-interval, QRS, QT interval, and QTc interval) will be performed and recorded.

For subjects enrolled into the marizomib arm prior to the implementation of protocol version 5, 12-lead ECG on Day 1 of the subsequent two cycles of adjuvant treatment within 15 minutes after end of MRZ infusion.

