- ^j For WOCBP, urine or serum pregnancy tests are to be done within 7 days of randomization and within 72 hours of treatment start
- ^k If baseline assessments have been done within 14 days of start of treatment, they do not have to be repeated for cycle 1 day 1
- ^l The first MRI scan should occur 4 weeks post end of RT; the 8-week imaging schedule will start after this scan
- ^m Brain MRI scan if one has not been done in the previous 4 weeks and no progression as yet been recorded
- ⁿ At disease progression
- ^o Frozen tissue sample will be collected at progression if the patient undergoes salvage surgery
- ^p Results of MRI scans done as part of standard of care will be collected, or done as per the study schedule of every 8 weeks (continuing on initial schedule) until disease progression
- ^q For all centers, MMSE every 16 weeks \pm 1 week until disease progression;
For participating centers, tests of objective neurocognitive function: HVLT-R, Trail Making Tests Part A & B and COWA and the MOS questionnaire on self-perceived neurocognitive function every 12 weeks \pm 2 weeks, until disease progression
- ^r Quality of life assessment (modified EORTC QLQ C30/BN20) every 16 weeks \pm 1 week until death or lost to follow up
- ^s G8 will be measured in all patients aged 70 years and above at baseline.[†]
- [†] For subjects on the marizomib arm, 12-lead ECG to be collected on following days and timepoints ONLY: at baseline within 7 days of randomization: on D1 of concomitant treatment within 15 minutes after end of MRZ infusion; on Cycle 2 Day 1 of adjuvant treatment after end of MRZ infusion; and as clinically indicated.

Marizomib (NPI-0052)

Statistical Analysis Plan v2.0. Protocol 1709-BTG

EORTC

^u For subjects enrolled prior to the implementation of protocol version 5., 12-lead ECG on Day 1 on the subsequent two cycles of adjuvant treatment within 15 minutes after end of MRZ infusion.

^v In marizomib arm only : C1D1 (first day of first adjuvant cycle) 2 mL within 10 minutes after end of infusion and 2 mL at 45 minutes following end of infusion. C1D8 2mL at 45 minutes following end of infusion.

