- Continuous variables for which a coding system exists (such as for laboratory data) will be recoded into categories (for adverse events, the grading scale specified in the protocol will be used). Whenever no specific scale exists, lab data will be categorized based on the normal range: for example, below the lower normal limit (when appropriate), within the normal range, above the upper limit of normal (ULN) and the degree to which it is above the ULN (for example > 2.5 x ULN, > 5 x ULN, > 10 x ULN). For laboratory data, the nadir is generally displayed. The nadir in a given cycle is the lowest laboratory value in that cycle; the overall nadir for a subject is the lowest laboratory value among all cycles;
- Other continuous variables (for example age, dose ...) are presented using the median range (minimum, maximum), IQR, mean and standard deviation;
- If appropriate, continuous data may also be presented in categories (for example, age may also be grouped in decades);

- P-values will be rounded to 3 decimal places. P-values that round to 0.000 will be presented as '<0.001' and p-values that round to 1.000 will be presented as '>0.999';
- Confidence intervals (CIs) will be presented as 2-sided 95% CIs unless specified differently in specific analysis;
- All mean and median values will be formatted to one more decimal place than the measured value. Standard deviation values will be formatted to two more decimal places than the measured value;
- All percentages will be rounded to whole numbers and one decimal. The number and percentage of responses will be presented in the form xx (xx.y%), where the percentage is in the parentheses;
- All listings will be sorted for presentation in order of treatment arm, subject, and date of procedure or event;
- All analysis and summary tables will have the analysis population sample size (ie, number of subjects);
- The day of the first dose of any study drug will be defined as Day 1.

Dealing with Multiple Values on the Same Day for Lab and Vital Signs Parameters

In cases where multiple values for the same variable are collected on the same visit (including baseline visit and post-baseline visits), the arithmetic average will be calculated and used as the value for that day for mean changes in laboratory and vital signs parameters.

Definition of Baseline Observation

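### SAP 12.4 summarises numeric QTc at three named visits only: other recorded QTc values have no place in it, and no output gives a per-patient maximum or a count above a cut-off

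*SAP*

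**What the plan says.** **Collection.** Protocol 5.6.4 schedules 12-lead ECGs in the marizomib arm at baseline, on Day 1 of concomitant treatment and on Day 1 of adjuvant Cycle 2, with more if clinically indicated. QTc is among the recorded measurements. The reason given for the additional ECGs is that a thorough "analysis of the QT/QTc data has not yet been submitted to the US FDA". The ECG footnotes to the schedule in SAP 5.1 repeat the arrangement: "on Cycle 2 Day 1 of adjuvant treatment after end of MRZ infusion; and as clinically indicated". For patients enrolled before protocol version 5 was implemented, they ask for a "12-lead ECG on Day 1 on the subsequent two cycles of adjuvant treatment within 15 minutes after end of MRZ infusion". These are called substitute ECGs below.

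**Analysis.** SAP 12.4 names three visits for the QTc summary: "The QTc-interval at baseline, Day 1 of concomitant treatment, Cycle 2 Day 1 of adjuvant treatment will be summarized, including change from baseline". It adds: "The average of the readings at each visit will be used for the summary". The section also plans a description of QT length by sex, a table of the overall ECG interpretation (normal; abnormal, not clinically significant; abnormal, clinically significant), and this per-patient output: "The shift from baseline to worst during the treatment in the overall ECG interpretation will be displayed in cross-tabulations for each treatment". Protocol 8.2.3.2 (Safety analysis) contains no ECG analysis.

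**General conventions.** SAP 6.1 reports continuous variables with their range: they "are presented using the median range (minimum, maximum), IQR, mean and standard deviation". It also says: "If appropriate, continuous data may also be presented in categories". A separate, mandatory rule in the same section recodes continuous variables into categories where a coding system exists, with laboratory data as the example.

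**The concern.** The extra ECGs were added because of an open QT/QTc question. The usual way to look at such a question is each patient's largest value and largest increase, and how many patients passed a marked level. A mean and a change from baseline by visit can look unremarkable while a few patients have long intervals.

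Neighbouring SAP sections do give per-patient worst outputs for quantitative safety data: worst grade for hematology (12.2.1) and biochemistry (12.2.2), and shift to worst against normal ranges for vital signs (12.3). For ECGs, worst applies only to the three-category interpretation.

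At stake is the completeness of a descriptive safety report. Followed exactly, the plan leaves some recorded QTc values out of the QTc summary and does not state how many patients had a marked value, apart from events that investigators reported.

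**Working it through.** The plan states no figure that could be reproduced. The check sets what is collected against what is summarised, then asks whether the number affected can be sized.

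**Step 1: where each recorded QTc value goes** (Protocol 5.6.4; SAP 5.1 footnotes; SAP 12.4)

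| ECG | In the QTc summary? |
|---|---|
| Baseline, concomitant Day 1, adjuvant Cycle 2 Day 1 | Yes |
| Clinically indicated | No place named |
| Substitute, next two cycles are 1 and 2 | Cycle 2 Day 1 yes; Cycle 1 Day 1 no |
| Substitute, next two cycles are 2 and 3 | Cycle 2 Day 1 yes; Cycle 3 Day 1 no |
| Substitute, patient already past Cycle 2 Day 1 | Neither (both at Cycle 3 Day 1 or later) |

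So every pre-version-5 marizomib patient who had both substitute ECGs has at least one value outside the summary.

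**Step 2: whether another output supplies a QTc maximum or count**

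- The shift to worst is per patient and not tied to visits, but it rates the overall interpretation.
- The description by sex is not tied to visits, but it concerns QT and names no maximum or cut-off.
- The range at a named visit shows the largest visit average there, not how many patients were high or what happened at other ECGs.
- The adverse-event tables (SAP 12.1.1) count patients by preferred term, but only for prolongation reported as an event.
- The two SAP 6.1 rules on categories do not name QTc, say which ECGs enter, or require a per-patient worst value.

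**Step 3: can the group already past Cycle 2 Day 1 be sized?**

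Inputs:
- 286 enrolled, 144 of them on marizomib, on 10 Jul 2019 (Protocol 1.1, read as referring to this trial).
- 616 randomised on 28 Apr 2020 (Protocol 8.3).
- Version 5.0 dated 22 Jan 2019 (Protocol document history).
- 150 patients planned for the first year (Protocol 8.1.1), which is 150 / 12 = 12.5 per month.

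Later accrual: (616 − 286) / 293 days = 330 / 9.63 months = 34.3 per month. From version 5.0 to 10 Jul 2019 is 169 days = 5.55 months.

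Randomisation to Cycle 2 Day 1: up to 1 week to start (Protocol 6.2), plus 6 weeks of radiotherapy, a 4-week break and a 4-week first cycle (Protocol 4), is 14 to 15 weeks = 3.22 to 3.45 months.

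Formula: patients past Cycle 2 Day 1 = enrolled at version 5 − accrual over the preceding 3.22 to 3.45 months. Multiply by 144/286 for the marizomib arm.

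- **34.3 per month throughout:** enrolled 286 − 5.55 × 34.3 = 95.7. The preceding 3.22 to 3.45 months would supply 110.4 to 118.3, more than that, so the result is 0.
- **34.3 after version 5.0, 12.5 before:** 95.7 − (40.3 to 43.1) = 52.5 to 55.4; on marizomib 26.5 to 27.9.
- **The same, with sites implementing one month later (assumption):** enrolled 286 − 4.55 × 34.3 = 129.9. Subtracting one month at 34.3 and the rest at 12.5 leaves 65.0 to 67.9; on marizomib 32.7 to 34.2.
- **25 per month from version 5.0 to July 2019 (assumption), 12.5 before:** enrolled 286 − 5.55 × 25 = 147. Less 40 to 43, this gives about 52 to 54 on marizomib. It implies a start about 147 / 12.5 = 11.8 months before version 5.0, around January 2018, which is after version 1.0 (13 Nov 2017).

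The answer moves from 0 to more than 50 with accrual rates the documents do not give. Patients who had stopped marizomib had no substitute ECG, which lowers it by an unknown amount. The number of clinically indicated ECGs is not given either.

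**The case against.** The strongest reply is that QT prolongation is already covered. The shift-to-worst table can take in substitute and clinically indicated ECGs and separates clinically significant abnormality. Adverse events include abnormal test findings (Protocol 16.1) and are tabulated by preferred term and for grades 3 and 4. An ECG done for a clinical reason is the kind most likely to come with a reported event. Keeping symptom-triggered ECGs out of a by-visit mean is sound practice. The mandatory SAP 6.1 recoding rule might also reach QTc, with the protocol's CTCAE version 5.0 as the coding system.

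Much of this stands. A reader might infer that the excluded ECGs are ignored altogether, or that marked prolongation would go unseen. The documents do not support that, because the shift table, the QT description and the adverse-event tables can each show some of it. A reader might also infer that this SAP was meant to be the thorough QT/QTc analysis. Protocol 5.6.4 says only that such an analysis had not been submitted and that more ECGs would therefore be collected.

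The reply does not close the gap. None of these outputs gives a numeric QTc maximum per patient or a count of measured values. Whether the recoding rule covers QTc cannot be settled from the documents. Even if it does, it leaves open which ECGs enter and whether the worst value per patient is used. Symptom-triggered ECGs can be handled by showing scheduled-only counts beside the all-ECG counts.

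**Conclusion.** The point holds as a minor gap in descriptive safety reporting. The rule in SAP 12.4 leaves clinically indicated QTc values, and substitute values other than Cycle 2 Day 1, without a place in the QTc summary. No output specifies a per-patient maximum, a maximum increase or a count above a cut-off. This rests on the wording of the plan and not on any accrual assumption.

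Its size in patients is unknown. A reader might take the first two accrual scenarios as bounds of 0 and 28, or think that only patients past Cycle 2 Day 1 are affected. Neither is supported: the last scenario roughly doubles the upper figure, and earlier patients also have a value at Cycle 1 or Cycle 3 that falls outside.

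There is no effect on overall survival or on any stopping decision. QTc prolongation is not an adverse event of special interest (SAP 12.1.3), and Protocol 5.6.4 reports no earlier ECG signal.

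**What to change.** In SAP 12.4, for marizomib-treated patients:

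1. Add an adjuvant post-infusion timepoint that includes all substitute ECGs.
2. Tabulate each patient's maximum post-baseline QTc and maximum increase from baseline, with counts above prespecified cut-offs. Show scheduled ECGs (including substitutes) and all ECGs side by side. Possible cut-offs are 450, 480 and 500 ms, and increases of 30 and 60 ms; these are proposals and do not come from the documents.
3. List the patients above the highest cut-offs.

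Label the output as descriptive and without a randomised comparator, because the on-treatment ECGs are scheduled only in the marizomib arm.

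The cost is one added timepoint, one table and one listing from data already recorded. Under SAP 3 the long-term follow-up report presents all of Section 12, so there is a planned report to carry them. The one drawback is that symptom-triggered ECGs raise the all-ECG counts, which is why the scheduled-only counts stand beside them.

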12.5. Pharmacokinetic Endpoints

The plasma concentration of MRZ will be described by the nominal time of collection using summary statistics based on the pharmacokinetics (PK) population. The PK population is defined as a collection of subjects who had at least one quantifiable plasma concentration of MRZ. As appropriate, the plasma concentrations may be used for exploratory exposure-response analyses of efficacy and safety endpoints. The analyses might be described in a separate analysis plan and reported separately.

If the number of samples collected is not sufficient only patient listings with PK data will be presented.

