silencing) consistently results in anti-glioma activity. Together, these data suggest that proteasome inhibition should result in synergistic activity against various glioma cells when combined with temozolomide or irradiation. Bortezomib has been assessed in phase 1 and 2 trials in patients with recurrent glioblastoma. However, there was no clear signal of clinical activity, most likely because the drug does not cross the blood brain barrier (BBB) (Ref. 34; Ref. 16). In contrast, data from several preclinical studies demonstrate the unique ability of marizomib to cross the blood brain barrier (BBB). In a study measuring the 20S proteasome activity in mouse whole brain lysates with either marizomib or bortezomib, brain proteasome activity was inhibited by marizomib from 41-52% to 94-98% (peak), while bortezomib had no effect on brain proteasome activity (Ref. 56). Second, in a quantitative whole-body autoradiography study in rats, after a single intravenous dose of radiolabeled marizomib, radioactivity was found throughout the central nervous system (CNS) (cerebrum, cerebellum, and medulla) from 2 min to 24 h after injection (Ref. 12). Thirdly, the proteasome activity in the prefrontal cortex of monkeys was reduced by 26-28% after once- or twice weekly oral doses of marizomib (MRZ) (Ref. 12). Finally, biweekly intravenous administration of marizomib to mice bearing intracranial glioma xenografts significantly prolonged survival in comparison with vehicle-treated controls (Ref. 12). Taken together, the clinical and preclinical data strongly support the conclusion that marizomib is brain penetrant. In clinical studies with MRZ IV, the duration of MRZ administration varied from 1 to 120 min over the dose range 0.025 to 0.9 mg/m^2. MRZ exhibited similar PK properties in both once and twice-weekly infusion studies, with a short t1/2 (generally ranging from 3 to 15 min), a very high volume of distribution, and a very high clearance rate. Together, these parameters account for the observation that little-to-no accumulation of MRZ is observed with repeat dosing. Generally, dose-proportional increases in MRZ exposure are noted with increased dose. The pharmacodynamic effects of MRZ on subunit-specific activity of the proteasome were measured in whole blood samples and mononuclear cells collected from patients with solid and hematologic malignancies across several clinical trials. Partial or complete inhibition of all three proteasome subunits [CT-L (chymotrypsin-like,  $\beta$  5); T-L (trypsin-like,  $\beta$  2) and C-L (caspase-like,  $\beta$  1)] was achieved with both once- and twice-weekly MRZ dosing, with the rank order of sensitivity (CT-L > T-L > C-L) consistent with the biochemical potency of MRZ (Ref. 46). For CT-L activity, both initial on Cycle 1, Day 1 (C1D1) and peak proteasome inhibition was dose-dependent, with complete (100%) inhibition of CT-L activity in packed whole blood (PWB), and maximal (60 to 80%) inhibition of CT-L activity in peripheral blood mononuclear cells (PBMC), within the first dosing cycle. In contrast, C-L and T-L activities were unchanged or increased in the first cycle of MRZ dosing, suggesting compensatory hyperactivation in response to effective blockade of CT-L activity. Importantly, this response was overcome by further treatment with MRZ, with inhibition of T-L and C-L activity noted across dose levels with repeated dosing. These data suggest that initial potent inhibition of CT-L activity leads to a compensatory hyperactivation of the C-L and T-L subunits. As CT-L activity becomes fully inhibited by the irreversible activity of MRZ, progressive inhibition of the hyperactivated C-L and T-L subunits occurs, ultimately resulting in robust pan-proteasome inhibition within 2 cycles in the majority of patients (Ref. 27). As of 01 August 2018, a total of 451 subjects have received one or more doses of MRZ in 7 Phase 1 and Phase 1/2, dose-escalating clinical studies evaluating MRZ as a single agent or in combination with other anticancer drugs, including 171 subjects in Phase 1b and Phase 1/2 clinical studies for newly diagnosed and recurrent glioblastoma, respectively. In patients with *recurrent glioblastoma*, marizomib was administered (10 minute infusion) as a single agent or in combination with bevacizumab (Study MRZ-108, NCT02330562); the study was conducted in 4 parts. In all 4 parts of the study, patients were at their second or third relapse and were required to have had documented progressive disease and no prior therapy with bevacizumab. Part 1 evaluated MRZ at escalating doses, in order to establish the recommended dose, in combination with BEV (Cohorts 1 to 3) with an expansion cohort (Cohort 4) in subjects with relapsed GBM. The Part 2 portion of the study explored the activity of single-agent MRZ (Cohort 5) at the recommended dose of 0.8 mg/m^2. Upon evaluation of the efficacy data in conjunction with the safety data from Cohorts 1 to 4, the decision was taken to attempt an inpatient dose-escalation of MRZ in order to evaluate higher doses in combination with BEV in the Part 3 portion of the study (Cohort 6) in the same patient population. Part 4 of the study was added to assess the feasibility of enterally-administered MRZ.

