### 6.2.2 During TMZ maintenance ± MRZ

The following assessment should be done before every cycle start (within 3 days before)

- physical examination (including weight)
- Karnofsky Performance Status (KPS) scale (Appendix E)
- vital signs (heart rate, temperature, blood pressure)
- concomitant medications and procedures
- adverse events
- hematology as in section 6.1
- biochemistry as in section 6.1
- For WOCBP, urine or serum pregnancy tests

At Cycle 1 marizomib arm only, pharmacokinetics.

\* At Cycle 1 D 1 (first day of the first adjuvant cycle): first blood sample for pharmacokinetics immediately after end of MRZ infusion and second sample within 45 minutes after end of MRZ infusion.

\* At Cycle 1 D 8: sample within 45 minutes after end of MRZ infusion.

At Cycle 2 Day 1 marizomib arm only

- a 12-lead ECG within 15 minutes after end of MRZ infusion.

Every 8 weeks (± 7 days)

- Brain MRI scans. The first scan should occur 4 weeks post end of RT. The 8-week imaging schedule will start after this scan.  
All scans are to be uploaded on the EORTC imaging platform. For detailed acquisition parameters, see the study specific imaging guidelines.

Every 12 weeks ( $\pm$  7 days) after start of maintenance phase

- translational research:
  - Mandatory: 10 mL blood draw for plasma and 10 mL blood draw for serum
  - Optional: 10 mL blood draw for extracellular vesicles and 20 mL for PBMC

Every 16 weeks ( $\pm$  7 days)

- MMSE and Quality of life assessment (modified EORTC QLQ C30/BN20)

Every 24 weeks ( $\pm$  7 days)

- For participating centers, tests of objective neurocognitive function: HVLT-R, Trail Making Tests Part A & B and COWA and the MOS questionnaire on self-perceived neurocognitive function (Appendix J)

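### Marizomib concentrations are to be summarised by nominal time, but the protocol and SAP disagree on when samples are drawn, and the permitted window spans 3 to 15 half-lives

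*SAP*

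**What the plan says.** Protocol 8.2.3.3 leaves the pharmacokinetic analysis to the SAP. SAP 12.5 specifies: "The plasma concentration of MRZ will be described by the nominal time of collection", with summary statistics in the pharmacokinetic population. It adds: "The PK population is defined as a collection of subjects who had at least one quantifiable plasma concentration of MRZ". It permits optional, exploratory exposure-response use of the concentrations, possibly under a separate plan, and falls back to listings if too few samples are collected. It is silent on actual sampling time, on tolerance, on off-time samples and on values below quantification.

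The sampling instructions for the first adjuvant cycle are:

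- Protocol 6.2.2, Day 1: "first blood sample for pharmacokinetics immediately after end of MRZ infusion and second sample within 45 minutes after end of MRZ infusion".
- Protocol 6.2.2, Day 8: "At Cycle 1 D 8: sample within 45 minutes after end of MRZ infusion".
- SAP 5.1, schedule footnote v, Day 1: "2 mL within 10 minutes after end of infusion and 2 mL at 45 minutes following end of infusion". The same footnote puts the Day 8 sample at 45 minutes.

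Protocol 1.1 describes the half-life of marizomib as "generally ranging from 3 to 15 min".

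**The concern.** A nominal-time summary works when timing error is small relative to the half-life. Here the protocol sets an upper limit where the SAP sets a time point, and that limit is 3 to 15 half-lives after the end of infusion. A site following the protocol could draw the second Day 1 sample at 8 minutes. That sample would fall inside the SAP's window for the first sample but be tabulated at 45 minutes.

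At stake is the meaning of the descriptive concentration table. Its mean and spread could reflect when blood was drawn rather than how much drug was present. SAP section 3 says that section 12 will be presented in full in both the primary and the long-term follow-up reports, so the table would appear in each unless the listings fallback applies.

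**Working it through.** The documents give no concentration, assay limit or sample-size figure for pharmacokinetics, so there is no stated result to reproduce. The check asks how far apart two compliant draws can be.

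**Inputs.** Half-life t½ of 3 to 15 minutes (Protocol 1.1). Window of 0 to 45 minutes for the second Day 1 sample and the Day 8 sample (Protocol 6.2.2). Window of 0 to 10 minutes for the first Day 1 sample (SAP 5.1, footnote v).

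**Assumption.** First-order, single-exponential decline from the end of infusion. The documents do not state this.

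**Formula.** Ratio of concentrations for draws Δ minutes apart = 2^(Δ / t½).

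| Draws compared (min) | Δ | t½ = 15 min | t½ = 3 min |
|---|---|---|---|
| 0 v 45, full protocol window | 45 | 2^3 = 8 | 2^15 = 32,768 |
| 10 v 45 | 35 | 2^2.33 = 5.0 | 2^11.67 = 3,251 |
| 15 v 45, illustrative | 30 | 2^2 = 4 | 2^10 = 1,024 |
| 0 v 10, SAP window for first sample | 10 | 2^0.67 = 1.6 | 2^3.33 = 10 |
| 40 v 50, illustrative tolerance | 10 | 1.6 | 10 |

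**Effect on a summary.** Suppose, purely as an assumption, that draws were spread evenly over 0 to T = 45 minutes. With k = ln 2 / t½, relative to the end-of-infusion level:

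- Mean = (1 − e^(−kT)) / (kT).
- Mean square = (1 − e^(−2kT)) / (2kT).
- True 45-minute value = 2^(−45 / t½).

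For t½ = 15, kT = 2.079. The mean is 0.875 / 2.079 = 0.421 and the true value is 0.125. The tabulated mean is 0.421 / 0.125 = 3.4 times the true 45-minute value. The mean square is 0.984 / 4.159 = 0.237, so timing alone gives a coefficient of variation of √(0.237 − 0.177) / 0.421 = 58%.

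For t½ = 3, kT = 10.40. The mean is 0.0962 against a true value of 0.0000305, a ratio of about 3,150, and the coefficient of variation is 205%.

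The long half-life is the favourable case, and it still gives an 8-fold range across the window.

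**The case against.** The strongest reply is that the text permits mixing but does not show it. Actual draw times are not in the documents. If every site drew within 5 minutes of the 45-minute mark, the spread would be the 1.6-fold to 10-fold of the last table row. The protocol's schedule table is also incomplete as available, so a more exact instruction there cannot be excluded. This stands: the table can mix values, and no more than that is established.

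A reader might infer several stronger things that the documents do not support.

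- *That exposure-response work on central nervous system toxicity would be distorted.* Protocol 1.3 links that question to pharmacodynamic data. In SAP 12.5, nominal time governs only the descriptive summary; nothing says that optional exposure-response work would use it.
- *That a formal pharmacokinetic objective is compromised.* Only the protocol summary lists pharmacokinetics as an objective. Protocol 2.1 lists pharmacodynamics, and SAP 4.2 lists neither.
- *That 45-minute values will probably be unquantifiable.* The decay model leaves 12.5% to 0.003% of the end-of-infusion level, but no assay limit or concentration is given. If low values were unquantifiable, the largest ratios could not appear in a table either, so those ratios are theoretical.
- *That the population definition materially selects for high exposure.* One quantifiable value admits a patient, and both documents schedule a sample at or soon after the end of infusion. Few exclusions may result. The missing rule for unquantifiable values remains a smaller, real gap.

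**Conclusion.** The concern holds in limited form. The protocol and SAP contradict each other on the timing of all three samples, and the SAP then summarises by nominal time without a tolerance. Under first-order decline with the stated half-life, the 0 to 45 minute window allows an 8-fold difference at 15 minutes, and far more at 3 minutes, among values under one label. The 8-fold figure is the safer one to rely on, because it uses the long end of the half-life range.

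The size of any actual error depends on draw times that the documents do not give. The affected output is a conditional, descriptive table; exposure-response use is optional and exploratory; overall survival is untouched. This is a minor point, worth correcting because the stated rule can yield a misleading summary and the correction is cheap.

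**What to change.** 1. Reconcile Protocol 6.2.2 with footnote v of the SAP 5.1 schedule for all three samples, and establish which instruction sites followed. Recruitment has closed, so this mainly settles what the label means.
2. In SAP 12.5, summarise and plot concentrations by actual elapsed time from the end of infusion. The documents do not confirm that draw times were recorded. If they were not, say so and give listings only.
3. Restrict any nominal-time table to a pre-stated tolerance and list the samples outside it. A range of 40 to 50 minutes is one illustration.
4. State how values below quantification are handled, and define the population as marizomib-treated patients with at least one evaluable sample, including those with only unquantifiable results.

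The cost is SAP wording and the use of draw times if they exist. The nominal-time table would hold fewer samples, and some samples that complied with the protocol would move to the listing.
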